8.2.4 End of Study

After the End of Study Visit, all patients evaluable for efficacy will be followed for survival status according to local practice (a visit or a telephone call) every 12 weeks up to a period of 12 months after first treatment administration to the last patient.

The study ends 12 months after first treatment administration to the last patient.

All biological samples (including tumor slides and block and excepting safety blood samples) collected along the study will be stored for a maximum of 10 years from the date of the last patient last visit. After 10 years, the samples will be destroyed, or a new IEC/IRB approval and informed consent will be requested to keep the samples for an additional time period.

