8.5.5.2 Secondary Endpoints

- **Preliminary antitumor activity**

Step 1 (solid tumors): is assessed in terms of Response Rate (RR), Disease Control Rate (DCR) and duration of response (DOR). RECIST 1.1 assessment will be performed using CT scan or MRI of the chest and abdomen (including adrenal glands). Any other areas of disease involvement should be additionally investigated based on signs and symptoms of individual patients. For the baseline assessment, CT scan or MRI should be performed no more than 6 weeks (4+2 weeks) before the treatment start. Follow-up assessment will be performed every 2 cycles during study treatment (within a window of -7/+3 days of the scheduled date and in any case before the study drug administration of the subsequent Cycle) until objective disease progression as defined by RECIST 1.1 or at the End of Study Visit. Any other site at which new disease is suspected should be appropriately imaged. If an unscheduled assessment is performed and the disease has not progressed, every attempt should be made to perform the subsequent assessments at their scheduled visits.

Step 2 (NHL): is assessed in terms of CR, PR, and DOR. Cheson Criteria assessment (The Lugano Classification, 2014) will be performed using CT/PET-CT scan or MRI of chest and abdomen (including adrenal glands). Any other areas of disease involvement should also be investigated based on signs and symptoms of individual patients. For the baseline assessment, CT/ PET-CT scan or MRI should be performed no more than 6 weeks (4+2 weeks) before the treatment start. Follow-up assessments will be performed every 2 cycles during study treatment (within a window of -7/+3 days of the scheduled date and in any case before the study drug administration of the subsequent Cycle) for a total of 8 cycles or until objective disease progression as defined by Cheson Criteria (The Lugano Classification, 2014) or at the End of Study Visit. Any other site at which new disease is suspected should be appropriately imaged. If an unscheduled assessment is performed and the disease has not progressed, every attempt should be made to perform the subsequent assessments at their scheduled visits.

- **Preliminary clinical efficacy**

Overall Survival is defined as the number of days between the first study drug administration and death from any cause. Patients without the event are censored to the last date of follow-up.

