8.6.8 Serious and Non-Serious Adverse Events Follow-up

After the End of Study Visit or 28 days after last study drug administration whichever occurs last, the Investigator is not requested to actively follow-up the patient unless ongoing SAEs or non-serious AEs of special interest (as per Cohort Review Committee) are present. However, if after the end of the study the Investigator becomes aware of any reportable SAEs, they should be duly reported to the Sponsor. These SAEs should be recorded in the eCRF if it is available. If the eCRF is not available, the paper SAE report form will be used as a backup.

Patients who discontinued the treatment for safety reason will be followed until the event disappears, the patient's condition stabilizes, or until recovery from all toxic effects and longer in case of expected delayed toxicity.

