9.2 ANALYSIS POPULATIONS

The following analysis population will be considered in the statistical analysis:

- **DLT population**

All patients receiving at least 75% of the first scheduled study drug administration and with a safety follow-up of 21 days after the administration. Patients enrolled in the dose escalation phase who are not DLT evaluable will be replaced.

- **Safety population**

All patients receiving at least 1 dose of study treatment.

- **Efficacy population**

All eligible patients who receive at least 2 complete treatment cycles and have at least 1 disease assessment are to be considered evaluable for efficacy.

- **Per-Protocol (PP) population**

All patients of the efficacy population excluding patients who experience major protocol violation(s) that may affect the efficacy analyses.

- **PK population**

All patients receiving study treatment and with reliable drug assay data relevant for the PK parameter of interest.

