9.3.3 Efficacy analysis

Efficacy analysis will be performed only through descriptive statistics.

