2. STUDY OBJECTIVES

2.1.1.1. PRIMARY OBJECTIVE

- To identify the MTD of MEN1309 when given as an IV infusion on Day 1 of a 21-day cycle in patients affected by CD205-positive solid tumors and NHL.

- To identify the DLT of MEN1309.

2.1.1.2. *SECONDARY OBJECTIVE*

- To assess the toxicity profile of MEN1309.
- To assess the pharmacokinetic (PK) profile after single and repeated doses of MEN1309 following IV administration.
- To determine the immunogenicity of MEN1309.
- To determine the preliminary clinical activity of MEN1309 in the overall treated population and in the Cohort expansion of TNBC patients

2.1.1.3. *EXPLORATORY OBJECTIVE*

- To determine the correlation between free CD205 with the clinical activity of MEN1309.
- To determine the correlation between CD205 expression on formalin-fixed and paraffin-embedded (FFPE) archived tissues samples and/or derived from new tumor biopsies and the clinical activity of MEN1309.
- To determine the deoxyribonucleic acid (DNA) sequence of CD205 at baseline.
- To determine the CD205 expression by flow cytometry on peripheral blood cells at baseline.
- Time course of CEA, CA 15-3 markers in the Expansion Cohort in TNBC patients

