e = Vital signs to be collected prior to study drug administration, every 15 minutes at Cycle 1 and every 30 minutes starting from Cycle 2 during the first hour of study drug administration and then at every hour until the end of infusion. In case of temporary infusion interruption, vital signs should be collected every 15 minutes until the first hour post-infusion re-start and then every hour until the end of infusion (or until 1-hour after the permanent infusion interruption).

f = 12-lead ECG record to be performed prior to study drug administration and 30 minutes after the end of the infusion; ECG will be also monitored during IV infusion up to 30 minutes after the end of infusion. If ECG monitoring equipment is not available, at Cycle 1 heart rate should be monitored up to 30 minutes after the end of infusion and 12-lead ECG recorded at 30, 60 and 120 minutes during the IV infusion with final 12-lead ECG record at 30 minutes after the end of infusion; starting from Cycle 2, heart rate should be monitored up to 30 minutes after the end of infusion with final 12-lead ECG record at 30 minutes after the end of infusion.

g = See “Blood Samples Flow Chart and PK Blood Samples Flow Chart” (Section 2.3 and Section 2.4) that includes blood sample collection for safety laboratory tests, β -HCG pregnancy test, Anti-HIV Antibodies, Anti-HBcAg antibodies, Anti-HBsAg antibodies, HBV-DNA, HCV-RNA tests, immunogenicity assessment, free CD205 assessment, flow Cytometry for CD205 expression and DNA sequence of CD205 assessment.

h = TLS Risk Assessment according to Investigator’s TLS manual, will be performed ONLY prior to study drug administration at Visit 1 (Day 1) of Cycle 1 (see [Appendix II](#)).

i = TLS prophylaxis should be given every cycle, if applicable (see [Appendix II](#)).

j = Mandatory premedication with an antihistaminic and an antipyretic (as per local practice) and dexamethasone 20 mg will be administered 30 to 60 minutes prior to study drug administration. Starting from Cycle 3, the dose of dexamethasone can be adjusted upon Investigator’s judgement.

k = After the End of Study Visit, all patients evaluable for efficacy will be followed for survival status according to local practice (a visit or a telephone call) every 12 weeks up to a period of 12 months after first treatment administration to the last patient.

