Summary statistics will also include the number and percentage of patients with Normal, Abnormal NCS (Non Clinically Significant) or Abnormal CS (Clinically significant), by parameter and visit. Shift tables will be presented with the counts of individual shifts from each of the reference range categories from baseline to post-dose by laboratory parameter, cohort and visit.

All laboratory data will also be reported in listings.

Previous/ Concomitant medication

All medication taken within 30 days before enrolment and taken during the study will be listed. Medication will be coded using the WHO drug dictionary (version C_DD_Jun2012-WithPrefTerm) and summarised by PT and by anatomical therapeutic chemical (ATC) category level X.

Previous medications are those which start within 30 days prior to enrolment and stopped prior to first dose of study drug. Concomitant medications are those which are started on or after date of first induction, or started prior to induction and stopped after or are ongoing.

The number and percentage of patients of previous and concomitant medication will be tabulated and summarized for concomitant medications.

Any previous and concomitant medication record will also be presented in a listing.

Electrocardiogram (ECG) Evaluations

ECG judgment collected on the eCRF will be summarised descriptively by cohort and visit. Similarly, changes from baseline for each post baseline visit will be summarised.

Vital Signs Evaluations, weight

Vital signs (systolic and diastolic BP (Blood Pressure - mmHg), weight reported in kilograms (kg), heart rate), will be summarised descriptively by cohort and visit. Similarly, changes from baseline will be summarised for all scheduled post baseline visits.

All vital signs parameters will be listed.

Physical Examinations

Physical examination findings (Normal, Abnormal NCS or Abnormal CS) will be summarised using descriptive statistics by Body System, cohort and visit.

Abnormal NCS or Abnormal CS findings on physical examination will be presented in a listing.

Efficacy Analyses

During CRC meeting no efficacy data can be analyzed since efficacy assessment (MRI TC PET scan) will be repeated every 2 cycle.

The efficacy will be evaluated at the end of the study.

Pharmacokinetics Analysis

Pharmacokinetics section will be present upon availability of laboratory data.

Plasma concentrations will be reported for each time point.

PK parameters will be reported with:

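### The efficacy set leaves out treated patients who do not complete two cycles, and planned survival follow-up covers only that set

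*Protocol*

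**What the plan says.** **Set definition.** Protocol 9.2 and SAP 6.1.1.3 use the same words: "All eligible patients who receive at least 2 complete treatment cycles and have at least 1 disease assessment are to be considered evaluable for efficacy". The Per Protocol set is a subset of this one.

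**Assignment.** Protocol 9.3.3 says "Efficacy analysis will be performed only through descriptive statistics", and the SAP efficacy paragraph (6.1.1.2) says "The efficacy will be evaluated at the end of the study". Neither names a set. By contrast, safety analyses are tied to the Safety population (protocol 9.3.4, SAP 6.1.1.2) and PK analyses to the PK population (protocol 9.3.2).

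**OS.** Protocol 8.5.5.2: "Overall Survival is defined as the number of days between the first study drug administration and death from any cause". Anyone not known to have died is censored at last follow-up. SAP 5.1.1.2 agrees.

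**Survival follow-up.** Protocol 8.2.4: "After the End of Study Visit, all patients evaluable for efficacy will be followed for survival status according to local practice". The same limit stands in the synopsis, the flow chart, 8.1 and 8.5.1, and in SAP flow-chart note k ("all patients evaluable for efficacy will be followed for survival status according to local practice"). For everyone else, protocol 8.6.8 says that after the End of Study Visit or 28 days after last dose, whichever is later, "the Investigator is not requested to actively follow-up the patient unless ongoing SAEs or non-serious AEs of special interest" are present. Patients who stop for safety reasons are followed until the event resolves or stabilises.

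**Objective.** SAP 2.1.1.2: "To determine the preliminary clinical activity of MEN1309 in the overall treated population and in the Cohort expansion of TNBC patients". Protocol 7.2 has the activity objective without that reference to treated patients.

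**The concern.** Membership of the Efficacy set depends on what happens after the first dose. Protocol 8.2.3 lists disease progression, a Cycle 1 DLT and a life-threatening related SAE among the reasons for withdrawal. Patients who stop before two cycles are therefore likely to include many treatment failures. Leaving them out raises RR and DCR, and it builds guaranteed survival time into an OS that starts at first dose.

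Switching to all treated patients does not fully repair OS, because survival contact is planned only for members of the Efficacy set. What is at stake is the description of preliminary activity, both overall and in the triple-negative breast cancer (TNBC) expansion of 25 planned patients (SAP 1). The same data would give different figures depending on the set.

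**Working it through.** The documents give no early-exit rate, response rate or survival assumption. There is no planned figure to reproduce, and every rate below is an assumption.

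**1. Response.** Let f be the share of treated patients who do not complete two cycles, none of them responding.

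Figure in the Efficacy set = figure in all treated / (1 - f)

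| f | factor | 10% RR reads | 40% DCR reads (no leaver has disease control) |
|---|---|---|---|
| 10% | 1.11 | 11.1% | 44.4% |
| 20% | 1.25 | 12.5% | 50.0% |
| 30% | 1.43 | 14.3% | 57.1% |
| 40% | 1.67 | 16.7% | 66.7% |

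The choice of all treated patients also needs a rule for missing scans, because protocol 9.3.5 applies observed cases. If a share h of leavers has an End of Study scan, the factor is 1/(1 - f(1 - h)). With h = 0.5, a 10% RR reads 10.5%, 11.1%, 11.8% and 12.5% for the four values of f. With h = 1 there is no inflation.

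For TNBC, three responders are 12.0% of 25 (exact 95% CI 2.5 to 31.2) and 15.0% of 20 (3.2 to 37.9).

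**2. Guarantee time.** Two 21-day cycles are 2 x 21 = 42 days, so about week 6. If two administrations suffice, the second falls on Day 22, so about week 3. The documents do not say which is meant. The scan due at Day 43 may be done 7 days early (protocol 8.5.1), at Day 36. It is unclear whether a patient who progresses on that scan counts as having two complete cycles.

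**3. Last planned contact for early leavers.** The End of Study Visit falls within 6 weeks of the last dose, and adverse events are recorded to at least 28 days after it.
- After one dose: Day 1 + 28 to 42 days = Day 29 to 43.
- After two doses: Day 22 + 28 to 42 days = Day 50 to 64.

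**4. OS illustration.** Completers are alive to week 6 and then exponential with median 39 weeks. Leavers are exponential from first dose with median mL.
- True, all treated: S(t) = f x 2^(-t/mL) + (1 - f) x 2^(-(t - 6)/39)
- All treated, leavers censored at week 6: [f x 2^(-6/mL) + (1 - f)] x 2^(-(t - 6)/39)
- Efficacy set: 2^(-(t - 6)/39)

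At f = 20%, mL = 13 and t = 26 weeks:
- True: 0.2 x 0.250 + 0.8 x 0.701 = 61.1%, median 35.9 weeks.
- Leavers censored: (0.2 x 0.726 + 0.8) x 0.701 = 66.2%, median 41.8 weeks.
- Efficacy set: 70.1%, median 45.0 weeks.

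The Efficacy set therefore reads 9.0 points high. With 3 weeks of guarantee time in place of 6, it reads 66.4% against a true 58.2%, or 8.3 points high before rounding.

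The censoring error alone is +5.2 points. It is +6.3 if leavers are censored at week 4 and +4.1 at week 9. For f from 10% to 40% it runs from +2.6 to +10.4 points. At f = 20% it falls to +1.9 points if mL is 26 weeks, to zero at 39 weeks, and to -1.2 points at 52 weeks.

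**The case against.** The strongest reply is that the plan is coherent. It defines an efficacy population, takes the Per Protocol set from it, and follows those same patients for survival. On that reading no set is in dispute, and the follow-up gap does not arise because OS is never reported more widely. This reading is the natural one, and I adopt it.

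A reader might infer that three sets compete: Efficacy, all treated, and the ITT default in SAP 8.1.1.2. The documents do not support that. ITT is not among the defined sets. It sits beside a table header with another study code (DELA-01) and a mention of tables by treatment and gender, so it looks like template text rather than evidence of intent. The treated-population wording in the SAP objective can mean all cohorts pooled, as opposed to the TNBC expansion. It is in tension with the Efficacy set but does not settle the choice. The list of tables is only a heading in the text available, and a table title may name the set.

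A reader might also infer that survival data on early leavers are certain to be lost. That goes too far. Deaths up to the End of Study Visit or 28 days after last dose, whichever is later, fall within adverse event recording (protocol 8.6.2). Safety discontinuations are followed longer, and nothing bars collecting vital status later.

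Two further replies stand. The eligibility criterion of at least 2 months' life expectancy argues against many deaths before week 6, although exits for progression or toxicity remain plausible. SAP 6.1.1.2 will show the size of each set and the reasons for discontinuation by cohort, so exclusions will be visible.

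Week 26 is not a planned time point; rates are planned every two cycles. At 24 weeks the same formulas give 0.2 x 0.278 + 0.8 x 0.726 = 63.7% true, 0.945 x 0.726 = 68.6% with leavers censored, and 72.6% in the Efficacy set. The picture is unchanged.

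None of this removes the conditioning on two cycles, and reporting set sizes does not correct it.

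**Conclusion.** The point holds as a selection problem. Read naturally, the plan reports efficacy only in patients who complete two cycles and have an assessment. RR and DCR are raised by up to 1/(1-f), a factor of 1.11 to 1.67 for assumed f of 10% to 40%. OS from first dose is conditional on reaching about week 6, or week 3 on the looser reading of two cycles.

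Reporting OS in all treated patients removes the conditioning but meets the follow-up gap. It would be wrong to claim that this gap always flatters OS: the sign depends on the prognosis of early leavers, and the error is zero if their later hazard equals that of the others.

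Severity is low to moderate. Efficacy is secondary and descriptive, the response shift in 25 TNBC patients is small against sampling error, and the MTD and DLT conclusions are untouched.

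**What to change.** 1. In protocol 9.3.3 and the SAP efficacy paragraph, report RR, DCR, PFS and OS in all treated patients (the Safety population), overall and for the TNBC expansion. Count treated patients without a post-baseline assessment as non-responders in the RR and DCR denominators, and state this as an exception to the observed-cases rule in 9.3.5. Keep the Efficacy and Per Protocol sets as supportive. Label OS in the Efficacy set as conditional on completing two cycles, and say whether that means two administrations or two 21-day periods.
2. Extend the 12-weekly survival contact to all treated patients. SAP 1 already refers to the end of the study, in mixed tenses. If follow-up has closed, report the number of early leavers, their last known-alive dates and the resulting limitation on OS.
3. Replace ITT in SAP 8.1.1.2 with the named set. This is a tidy-up.

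The cost is SAP wording, a short protocol amendment and a few extra contacts if follow-up is still open, and response figures that are likely to be somewhat less favourable.

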9.3 STATISTICAL ANALYSIS

9.3.1 Descriptive statistics

All study variables will be presented by dose-cohort and overall, using the appropriate descriptive statistics according to the variable nature, unless otherwise specified:

- Continuous variables: number of non-missing observations, arithmetic mean, standard deviation (StDev), standard error (SE; for PK variables), minimum, median, maximum (and geometric mean and its 90% confidence interval [CI] for PK variables).
- Categorical variables: number of non-missing observations and column percentages (N, %).

- Time to event variables: number of non-missing observations, number and percentage of censored observations, 1st quartile, median (and its 95% CI), 3rd quartile, Kaplan-Meier survival curves and event rate every two cycles, and at the End of Study Visit and at the End of Study, as appropriate.

The behavior over time of study variables will be summarized by treatment cohort and overall as follows:

- Continuous variables: descriptive statistics for each time point and for the absolute/percentage differences to baseline. For PK variables, only descriptive statistics for each time point will be used.
- Discrete variables: descriptive statistics for each time point and shift tables to baseline.

9.3.2 Pharmacokinetic Analysis

The PK analysis will be conducted on the PK population. All PK variables (i.e., serum concentrations and parameters) will be summarized by cohort using the following descriptive statistics:

- number of non-missing observations (N),
- arithmetic mean and its 95% CI, StDev, coefficient of variation (CV%), and SE,
- geometric mean (GM) and its 90% CI and GM CV%,
- minimum, median, maximum.

The concentration of MEN1309, tAb, DM4 and its metabolite S-methyl-DM4, when applicable, will be summarized for each scheduled sampling time point (see [§2.4](#)) using descriptive statistics. Individual serum concentration data versus time will be presented in a data listing and visualized as individual concentration-time plots. Additional analyses, if deemed appropriate, will be described in the statistical analysis plan.

For descriptive statistics, BLOQ concentrations at time zero, when the patient has not previously been dosed, will be set to zero. All other BLOQ values will be substituted by $\frac{1}{2}$ LLOQ value before the calculation of the summary statistics.

9.3.3 Efficacy analysis

Efficacy analysis will be performed only through descriptive statistics.

9.3.4 Safety analysis

Safety analysis will be performed on the safety population through descriptive statistics during each study phase. Summary statistics will report the incidence of the AEs by CTC toxicity grade, dose level, relationship to study drug and overall. Counts and percentages will be reported for the results

of ECG, laboratory values, vital signs, physical examination, all classified as Normal/Abnormal Not Clinically Significant (NCS)/Abnormal CS by dose level and visit.

Descriptive statistics will also be produced for the extent of exposure, overall drug administration, drug administration by dose level and dose delay by dose level.

9.3.5 Data imputations

Missing values will not be imputed since for every analysis an observed-cases approach will be applied.

